14. ADVERSE EVENTS, ADVERSE DEVICE EFFECTS AND DEVICE DEFICIENCIES

14.1 DEFINITION OF ADVERSE EVENT (AE) AND ADVERSE DEVICE EFFECT (ADE)

Adverse Event (AE): Any untoward medical occurrence, unintended disease or injury or untoward clinical signs (including abnormal laboratory finding) in subjects, users or other persons whether or not related to the IMD.

NOTE:

- This definition includes events related to the IMD or the comparator
- This definition includes events related to the procedures involved
- For users or other persons, this definition is restricted to events related to the use of the IMD or comparator.

Adverse device effect (ADE): AE related to the use of an IMD.

NOTE:

- This definition includes AEs resulting from insufficient or inadequate instructions for use, deployment, implantation, installation or operation, or any malfunction* of the IMD;
- This definition includes any event resulting from use error or from intentional misuse of the IMD.
- This includes comparator if the comparator is a medical device.

*Malfunction is defined as a failure of an IMD to perform in accordance with its intended purpose when used in accordance with the instructions for use or CIP.

Treatment-emergent AE (TEAE): AE that occurs or that worsens in severity after at least one dose of IMD has been administered/applied.

14.2 DEFINITION OF DEVICE DEFICIENCIES

Device Deficiency (DD) : Inadequacy of a medical device with respect to its identity, quality, durability, reliability, safety or performance.

NOTE:

- DD include malfunctions, use errors, and inadequate labelling.
- This definition includes DD related to the investigational medical device or the comparator.

14.3 DEFINITION OF A SERIOUS ADVERSE EVENT (SAE) OR SERIOUS ADVERSE DEVICE EFFECT (SADE) AND UNANTICIPATED SERIOUS ADVERSE DEVICE EFFECTS

Serious Adverse Event (SAE): AE that:

- Led to death
- Led to serious deterioration in the health of the subject, that either resulted in
 - ✓ A life-threatening illness or injury, or
 - ✓ A permanent impairment of a body structure or a body function, or

- ✓ In-patient or prolonged hospitalization, or
- ✓ Medical or surgical intervention to prevent life-threatening illness or injury or permanent impairment to a body structure or a body function
- ✓ Chronic disease
- Led to foetal distress, foetal death or a congenital abnormality or birth defect.

NOTE: Planned hospitalization for a pre-existing condition, or a procedure required by the CIP, without serious deterioration in health, is not considered a SAE.

Serious Adverse Device Effect (SADE): ADE that has resulted in any of the consequences characteristic of a serious adverse event .

Unanticipated Serious Adverse Device Effect (USADE): SADE which by its nature, incidence, severity or outcome has not been identified in the current risk assessment.

NOTE: Anticipated SADE (ASADE): an effect which by its nature, incidence, severity or outcome has been identified in the risk assessment.

14.3.1 Definition of the Severity of an Adverse Event

The intensity of each AE must be assessed by the investigator using one of the following categories, and recorded in the e-CRF:

- 1 = MILD: Event results in mild or transient discomfort, not requiring intervention or treatment and does not interfere with the patient daily activities;
- 2 = MODERATE: Event results in sufficient discomfort, may require an additional treatment, but does not interfere with the patient's daily activities;
- 3 = SEVERE: Event results in significant symptoms, may require an additional treatment, or a modification of this treatment (or hospitalisation) and may interfere with the patient's daily activities.

Caution: The term “severe” is used to describe the intensity (severity) of the event. This means it is not the same as “serious” used to describe the seriousness of SAE which is based on patient event outcome or action criteria usually associated with events that pose a threat to a patient’s life or functioning (see section 14.3 for having the definition of a SAE).

14.3.2 Causality Relatedness to the IMD

The investigator will assess the causality/relationship between the IMD and the AE and record that assessment in the e-CRF based on the following definitions (only one answer possible):

Each AE will be classified according to five different levels of causality:

1. Not related
2. Possible
3. Probable
4. Causal relationship

The sponsor and the investigators will use the following definitions to assess the relationship of the adverse event to the investigational device or the investigation procedures.

1. **Not related:** Relationship to the device or procedures can be excluded when:

- the event has no temporal relationship with the use of the device or investigation procedures;
- the adverse event does not follow a known response pattern to the medical device (if the response pattern is previously known) and is biologically implausible;
- the discontinuation of medical device application or the reduction of the level of activation/exposure - when clinically feasible - and reintroduction of its use (or increase of the level of activation/exposure), do not impact on the adverse event;
- the event involves a body-site or an organ that cannot be affected by the device or procedures;
- the serious adverse event can be attributed to another cause (e.g. an underlying or concurrent illness/ clinical condition, an effect of another device, drug, treatment or other risk factors);

In order to establish the non-relatedness, not all the criteria listed above might be met at the same time, depending on the type of device/procedures and the adverse event.

2. **Possible:** The relationship with the use of the investigational device or the relationship with procedures, is weak but cannot be ruled out completely. Alternative causes are also possible (e.g. an underlying or concurrent illness/ clinical condition or/and an effect of another device, drug or treatment). Cases where relatedness cannot be assessed, or no information has been obtained should also be classified as possible.
3. **Probable:** The relationship with the use of the investigational device or the relationship with procedures, seems relevant and/or the event cannot be reasonably explained by another cause.
4. **Causal relationship:** the adverse event is associated with the investigational device or with procedures beyond reasonable doubt when:
 - the event is a known side effect of the product category the device belongs to or of similar devices and procedures;
 - the event has a temporal relationship with investigational device use/application or procedures;
 - the event involves a body-site or organ that
 - o the investigational device or procedures are applied to;
 - o the investigational device or procedures have an effect on;
 - the adverse event follows a known response pattern to the medical device (if the response pattern is previously known);
 - the discontinuation of medical device application (or reduction of the level of activation/exposure) and reintroduction of its use (or increase of the level of activation/exposure), impact on the adverse event (when clinically feasible);
 - other possible causes (e.g. an underlying or concurrent illness/ clinical condition or/and an effect of another device, drug or treatment) have been adequately ruled out;
 - harm to the subject is due to error in use;

In order to establish the relatedness, not all the criteria listed above might be met at the same time, depending on the type of device/procedures and the adverse event.

The sponsor and the investigators will distinguish between the adverse events related to the investigational device and those related to the procedures (any procedure specific to the clinical investigation). An adverse event can be related both to procedures and the investigational device.

Complications caused by concomitant treatments, not imposed by the clinical investigation plan, are considered not related. If routine procedures are not imposed by the clinical investigation plan, complications caused by them are also considered not related.

In some particular cases the event may not be adequately assessed because information is insufficient or contradictory and/or the data cannot be verified or supplemented. The sponsor and the investigators will make the maximum effort to define and categorize the event and avoid these situations. Where an investigator assessment is not available and/or the sponsor remains uncertain about classifying the adverse event, the sponsor should not exclude the relatedness; the event should be classified as "possible" and the reporting is not delayed.

Particular attention shall be given to the causality evaluation of unanticipated serious adverse events. The occurrence of unanticipated events related could suggest that the clinical investigation places subjects at increased risk of harm than was to be expected beforehand.

14.4 RECORDING AES

AEs recording and reporting will extend from signing of informed consent until the final visit. If the investigator is aware of an AE occurring within one month after final investigation visit and that he considers there is a causal relationship with the IMD, the AE should be recorded in the e-CRF.

The investigator shall:

- a) Record all AEs, regardless of the relationship to IMD, in the e-CRF, together with an assessment.
- b) Report to the Sponsor, without unjustified delay, all serious AEs; this information shall be promptly followed by detailed written reports.
- c) Supply the Sponsor, upon Sponsor's request, with any additional information related to the safety reporting of a particular event.

All AE reports should contain: a brief description of the event (diagnosis, localisation ...) date and time of onset (if needed), duration (hours or days), intensity of symptoms (severity), treatment required, relationship with IMD and CIP procedure, action taken with the IMD, outcome, date and time of resolution and whether the event is classified as serious.

If there is a worsening of a medical condition that was present before starting the clinical investigation, this should be considered as a new AE and a complete evaluation should be recorded.

14.5 REPORTING OF SAE

Reporting by the investigator to the Sponsor

In case of SAE, the investigator must:

Complete the relevant e-CRF pages and the SAE form with all available initial information.
within 24 hours of being aware of it

a SAE paper form [REDACTED] will have to be completed, dated and signed by the investigator and send by email [REDACTED] or by fax [REDACTED]

The initial report must be as accurate as possible, including details of the current illness, an assessment of the causal relationship between the event and the IMD. Additional follow-up reports must be sent back to Laboratoires THÉA within 24 hours upon receipt of follow-up information query.

In addition, the following information have to be recorded in the appropriate sections of the e-CRF:

- Demography
- Medical and surgical history
- Previous and concomitant medication
- Investigational medication administration record

The investigator is responsible for ensuring the follow-up of any patient who experiences a SAE during the investigation. The investigator or an appropriate qualified physician must re-examine the patient at regular intervals until completion of the Last Patient Last Visit. Further follow up information will be reported to Laboratoires THÉA.

If the investigator is aware about any SAE occurring **within 1 month after the final visit** and that he considers that it is related to the IMD, and therefore deemed as a possible SADE, the investigator must report the SAE to the Sponsor immediately.

As for all other investigational documents, the investigator will retain a copy of the SAE form as per regulatory requirements/for at least 10 years after the last device has been placed on the market.

Reporting by the Laboratoires Théa through CRO to Competent authorities/Ethics Committees

Laboratoires THÉA must report to the National CAs where the clinical investigation has commenced:

- a SAE **that has a causal relationship with the investigational device**, which indicates an imminent risk of death, serious injury, or serious illness and that requires prompt remedial action for other patients, users or other persons or a new finding to it: immediately, but **not later than 2 calendar days after**

Note: Member States may also require separate reporting to the Independent Ethics Committee(s) (IEC) and/or separate reporting to the other clinical investigators/ centers involved in the clinical investigation.

- any other SAE **that has a causal relationship with the investigational device**: immediately, but not later than 7 calendar days following the date of awareness by the sponsor of the new reportable event or of new information in relation with an already reported event.

After consultation with Laboratoires THÉA, the investigator may be required to provide information about certain SAE to the IEC according to the institutional policy.

14.6 REPORTING OF DEVICE DEFICIENCIES

If the investigator observes any abnormality and/or deficiency of T2769 the investigator must report to Laboratoires THÉA **within 24 hours of being aware of it** [REDACTED].

Laboratoires THÉA must

- review all DD and determine and document in writing whether they could have led to a SAE; in case of disagreement between the sponsor and the principal investigator(s), the sponsor shall communicate both opinions to concerned parties
- report to regulatory authorities/EC/investigators, within the required time period, **any device deficiencies that might have led to a serious adverse event if appropriate action had not been taken, intervention had not occurred, or circumstances had been less fortunate.**

Once Laboratoires THÉA is made aware of any deficiency with any components of the IMD and in function of the type of deficiency, the Laboratoires THÉA will take the appropriate decision to maintain the security/safety of patients.

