6.1.2.2 Masking and Code Breaking

Serious biases may occur in a clinical investigation including investigator bias (which may arise due to knowledge by the investigator of treatment allocated to a particular patient), evaluator bias and placebo effects. To protect an investigation against these potential biases, masking will be used.

This will be an investigator-masked clinical investigation.

The **masked investigator** will remain masked to the IMD (T2769 – Vismed® Multi). He/She will not receive the returned IMD from the patients.

The following-up and the number of returned IMDs will be recorded by **unmasked collaborator** throughout the clinical investigation.

The unmasked collaborator will also be in charge of returned/unreturned IMD (T2769 – Vismed® Multi) counting.

Masking will be achieved by coding the interventions, providing each product unit with identical cardboard box and by identifying it by an IMD kit number.

The code should not be broken except:

- in case of medical emergency (where knowledge of the IMD received would affect the treatment of the emergency),
- or when it is a regulatory requirement (e.g., for Unanticipated Serious Adverse Device Effect [USADE]).

The investigator is responsible for accessing the IRT System to obtain the name of the IMD received by the patient.

If an emergency code breaking becomes necessary, the investigator should notify the Sponsor.

When a code is broken, the date, time and reason must be recorded in the patient's Source, and in any associated AE report. The identity of the IMD should not be disclosed in these documents.

Further to a USADE assessment by the Global Drug Safety & Medical Information Department, the code might be broken for reporting purposes. The relevant Laboratoires THÉA, Contract Research Organization (CRO) and masked investigator and masked staff remain unaware of the identification of the IMD as per the above-mentioned process.

The overall randomisation list will be broken for data analysis after database lock.

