6.1.2.3 Dispensing

IMD will be dispensed by the masked collaborator and/or pharmacist delegate for selected tasks. Each IMD dispensation will be recorded in the related documentation.

During the whole investigation treatment period, the **masked investigator and/or delegate** will remain masked to the IMD (T2769 – Vismed® Multi). He/she will not receive the returned IMD from the patients.

All information regarding the usage of the IMDs will be contained in the package given to patients.

The IMDs must be dispensed only to patients in accordance with the Clinical Investigational Plan (CIP) and the randomisation.

Once all screening criteria have been checked, the patient will receive a box including Run-in Hydrabak® treatment for the run-in period.

At the randomisation visit#2 (Day 1), once inclusion and exclusion criteria have been checked and once the patient is eligible, the randomisation will be performed and the IRT will provide the IMD kit number allocated to the patient.

At the other visit (visit#3, Day 15 days \pm 1 day after the randomisation) with dispensation, the IRT will provide the IMD kit number allocated to the patient.

Two dispensations will be performed as follows:

- At randomisation visit#2(Day 1): one box containing enough bottles for the treatment period Day 1 to Day 15 \pm 1 day will be provided by the investigator (or delegate) or pharmacist with the number assigned by the IRT.
- At Visit#3 (Day 15): one box containing enough bottles for the treatment period Day 15 \pm 1 day to Day 36 + 3 days will be provided by the investigator (or delegate) or pharmacist with the number assigned by the IRT.

The site team member will instruct patient on the method of instilling the doses and will train his / her patient to not disclose the IMD characteristics neither during the visit not when reporting / discussing AE / Device Deficiency (DD).

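### Section 14.6 limits the 24-hour device-deficiency report to T2769, a condition the masked investigator is not meant to know is met, and sets no deadline for comparator deficiencies

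*Protocol*

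**What the plan says.** Protocol section 14.6 opens with the investigator's duty: "If the investigator observes any abnormality and/or deficiency of T2769 the investigator must report to Laboratoires THÉA". The time limit is "within 24 hours of being aware of it". The rest of the section sets sponsor duties that are not restricted to T2769. The sponsor reviews all deficiencies for whether they could have led to a serious adverse event (SAE), reports those that might have done so, and acts on a deficiency in any component of the IMD.

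On scope, section 14.2 states: "This definition includes DD related to the investigational medical device or the comparator".

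On masking, section 6.1.2.2 says that the masked investigator "will remain masked to the IMD (T2769 – Vismed® Multi"), and section 6.1.2.3 repeats this for the investigator or delegate throughout the treatment period. Neither receives returned product. Section 6.1.2.3 also has patients trained "to not disclose the IMD characteristics neither during the visit not when reporting / discussing AE / Device Deficiency (DD").

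Section 6.1.4 puts device deficiency on the masked investigator's or delegate's list at Visits 3 and 4. The unmasked collaborator's listed task at those visits is to record returned product.

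**The concern.** A reporting rule should turn on something the reporter can see. Here the reporter is the investigator, who is masked, yet the rule applies only if the faulty product is T2769. The protocol also tells patients to keep the product's characteristics to themselves when they describe a deficiency. The one fact that decides whether the clock applies is therefore the fact the masking sections withhold.

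The second difficulty is scope. A deficiency of Vismed Multi meets the definition in 14.2 and falls under the sponsor's review in 14.6, but no deadline brings it from the site to the sponsor. The review looks for problems that might have led to an SAE, so it works best when reports arrive before any harm. If sites read the text literally, the two arms would also be reported on different terms, and a comparison of deficiencies between arms would be harder to interpret.

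**Working it through.** The plan gives no figure to reproduce here. The check sets the sections side by side.

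| Question | Where | Answer |
|---|---|---|
| Which product triggers the 24-hour duty? | Protocol 14.6 | T2769 only |
| When does the clock start? | Protocol 14.6 | When the investigator becomes aware |
| Which products can have a deficiency? | Protocol 14.2 | Investigational device or comparator |
| Which deficiencies does the sponsor review? | Protocol 14.6 | All |
| Who collects deficiencies at visits? | Protocol 6.1.4, Visits 3 and 4 | Masked investigator or delegate |
| Does that person know the product? | Protocol 6.1.2.2, 6.1.2.3 | No |
| Is a deficiency a listed reason to break the code? | Protocol 6.1.2.2 | Not by itself |
| Is there another 24-hour rule? | Protocol 14.5 | Yes, for SAEs, with no product limit |
| Is there another timing rule? | Protocol 6.5.3 | e-CRF to be completed as soon as possible after the visit; no fixed limit |

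**Step 1, can the trigger be applied?** Rows 1, 5 and 6 do not fit together. The duty needs knowledge of the product, and the person collecting the deficiency is kept from it. The exceptions for breaking the code are "in case of medical emergency (where knowledge of the IMD received would affect the treatment of the emergency") or a regulatory requirement, for which the protocol's example is an unanticipated serious adverse device effect. An ordinary deficiency is neither, so the code-break route is not there to settle the question.

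**Step 2, what covers a comparator deficiency?** If it has caused an SAE, section 14.5 applies and the limit is 24 hours. If it has not, sections 6.1.4 and 6.4.1.3 have it collected and 14.6 has the sponsor review it, but no section gives a fixed site-to-sponsor limit. The gap is exactly this case.

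**Step 3, does the term IMD close the gap?** No, because its use varies. Section 6.4.1.3 and SAP section 2.2.1 use it for either product, while sections 14.1 and 14.2 set it against the comparator. The investigator's sentence in 14.6 does not use the term at all; it names T2769.

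**Step 4, scale.** Planned number randomised: 250 (Protocol 6.3.8). Allocation: 1:1 (Protocol 6.1.2.1).

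- Patients outside the duty as written: 250 × 1/2 = 125.
- At 4 bottles of assigned product each (Protocol 6.2.4): 125 × 4 = 500 bottles.

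These count patients and bottles, not deficiencies. The documents give no deficiency rate for either product.

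**The case against.** The best defence is that the rule works in practice. A masked investigator who cannot rule out T2769 can report every deficiency within 24 hours, which satisfies 14.6 and needs no unmasking. Comparator deficiencies are collected without product restriction, the sponsor must review all of them, and one that causes an SAE is already on a 24-hour clock. The protocol also plans for masked discussion of deficiencies: patients are trained not to reveal product characteristics, and unmasked staff or the pharmacist handle returned product. All of this stands, and it keeps the point small. It does not remove it. The text nowhere tells sites to report everything, and about 40 sites in 9 countries (Protocol 6.1.7) should not each have to infer it.

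A reader might infer three stronger things, and the documents support none of them.

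- *Comparator reports are delayed by the gap between visits.* The clock runs from awareness. A fault that the patient first mentions at a visit has waited equally long in either arm, and would still do so after the wording is corrected.
- *About half of all deficiencies escape expedited review.* That needs equal deficiency rates in the two arms. No rates are given, and section 6.1.1 says that the commercial packaging differs.
- *The rule must end in unmasking, lost reports or guesswork.* Reporting everything avoids all three, and a deficiency alone is not a listed ground for breaking the code.

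**Conclusion.** The point holds as an internal inconsistency. The 24-hour duty in section 14.6 is narrower than the definition in 14.2 and the sponsor's review in 14.6, and it depends on product identity that section 6.1.2.2 withholds from the investigator. Its effect is confined to the site-to-sponsor deadline for comparator deficiencies that have not caused an SAE, in an arm of about 125 of 250 patients. How many deficiencies that involves, or how late they would reach the sponsor, cannot be estimated from the documents.

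The primary endpoint, non-inferiority margin, error rate and sample size are unaffected. The correction is still worth making, because it is cheap and improves both safety reporting and even capture between arms.

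One assumption: the redaction after the 24-hour clause in 14.6 is taken to hide contact details, as the redactions in 14.5 and 14.8 appear to. The visible clause is complete before it and names only T2769.

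**What to change.** Reconcile section 14.6 with 14.2 and 6.1.2.2. In the investigator's sentence, replace the reference to a deficiency of T2769 with *deficiency of the assigned IMD (T2769 or Vismed Multi), identified by kit number*. Keep the existing limit of 24 hours from awareness, and add that the report must not disclose product identity. Name both products; IMD alone would leave the ambiguity, since 14.1 and 14.2 distinguish it from the comparator.

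Because the packaging differs, some descriptions could identify the product. Allow the existing unmasked collaborator to send the report in those cases.

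The cost is a one-sentence change, taken through the amendment process in section 9, and a few more expedited reports. If the unmasked collaborator is to send reports, that task should be added to the role's listed duties, which at present concern following up, counting and recording returned product.
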